11.2. Sample Size Determination

11.2.1. Efficacy

Under the following assumptions:

- a VE for Case Definition #2 of 70%
- and an incidence of Case Definition #2 of 0.75% in placebo recipients during the RSV season, assuming vaccination occurs before the RSV season
- 3 primary endpoints which are nested (see Section 11.4.1)
- a 1-sided α of 5% (total: as described in Section 11.4.1.1, corrections are performed for multiple endpoints and for IAs outlined in Section 11.12)
- 10% of exclusions (due to drop-out, major protocol deviations, etc.)

Simulations performed in R show that for a NH only study, 2,750 participants per vaccination group result in 80% total power to demonstrate $VE > 0$ for Case Definition #2 at the end of the RSV season, resulting in a total sample size of 5,500 participants. The end of the first RSV season is then defined as the end of the NH RSV season.

In case recruitment is not completed in the NH (and less than 18 RT-PCR-confirmed RSV-mediated LRTD events (using Case Definition #2) are observed in the NH before opening sites in the SH), enrollment will continue in the SH. As there is the possibility to have an early IA during the NH or SH RSV season (see Section 11.12), an additional 150 participants per vaccination group is needed to have 80% total power to demonstrate $VE > 0$ for Case Definition #2 at the end of the RSV season. The end of the first RSV season is defined as the end of the SH RSV season in case the study is performed at both hemispheres. So, if recruitment is spread over 2 hemispheres, the total sample size will be 5,800 participants.

With respect to Case Definitions #1 and #3, further simulations showed that the power to obtain a significant result for any case definition, after multiplicity correction that control the type I error at 5%, tended to be similar or better than for Case Definition #2 alone, without multiplicity correction. This result was valid over a broad range of incidence and vaccine efficacies, unless the VE for the most common case definition (Case Definition #3), was $> 20\%$ lower than the VE for Case Definition #2. Case Definition #2, which incidence lies between that of Case Definition #1

and #3, was chosen as basis for the power calculations and decision rule, as more prior information was available for this case definition in the literature. Under the assumptions described above, it is expected to observe 26 cases.

Under conditions described in Section 11.12 (less than 18 RT-PCR-confirmed RSV-mediated LRTD events by the end of the first RSV season for Case Definition #2, with a negative IA performed by the IDMC but a conditional power of 60% or more), 2,000 new participants may be vaccinated at the beginning of the second RSV season who will be followed up for one RSV season. This will increase the total power of the study to approximately 82%.

The operating characteristics of the methods used with the sample size are described in a separate modeling and simulations report.

11.2.2. Immuno Subset

Immunogenicity will be assessed in the Immuno Subset, ie, approximately 200 participants, of whom ~100 are active study vaccine participants. Approximately 25% of participants in the Immuno Subset in each region will be at increased risk of severe RSV disease.

Table 6 shows the actual distance from the mean to the limits of 95% CI around the actual value at Day 15 for different assays, accounting for 10% of exclusions with the current sample size for the Immuno Subset.

Table 6: Distance from the Mean to the Limits of 95% CI for Pre-F ELISA, VNA, and ELISpot

N (Active Group)	Pre-F ELISA (SD=1.3)		VNA (SD=1.5)		ELISpot (SD=1.2)	
	Distance ^a from Mean to Limits	95%CI if Observed Mean is eg, 6,000	Distance ^a from Mean to Limits	95%CI if Observed Mean is eg, 6,500	Distance ^a from Mean to Limits	95%CI if Observed Mean is eg, 400
All	100	0.272	(4,969;7,245)	0.314	(5,229;8,080)	0.251
Increased Risk	25	0.576	(4,025;8,944)	0.665	(4,099;10,306)	0.532

CI = confidence interval, ELISA = enzyme-linked immunosorbent assay, ELISpot = enzyme-linked immunospot, SD = standard deviation, VNA = virus neutralization assay

^a Calculated on the log₂-scale.

11.2.3. Safety Subset

While mild to moderate vaccine reactions (local injection site, systemic responses) are expected, AEs that preclude further vaccine administration (if applicable) are not anticipated.

With ~350 active study vaccine participants in the Safety Subset, the observation of 0 events in the database would be associated with 95% confidence that the true rate is less than 1%. For SAEs, which will be captured in all participants, the observation of 0 events in the database would be associated with 95% confidence that the true rate is less than 0.1%.

In addition, a cap will be installed to ensure that 350 participants in the Safety Subset (~175 in each group) are at increased risk for severe RSV disease. With 175 active study vaccine

participants at increased risk of severe RSV disease in the Safety Subset, the observation of 0 events (solicited or unsolicited) in the database would be associated with 95% confidence that the true rate in participants at increased risk of severe RSV disease is less than 1.7%.

SAEs will be captured in all participants. Outside the Safety Subset and Immuno Subset, no cap is installed on the number of participants at increased risk of severe RSV disease. It is expected that participants at increased risk for severe RSV disease will represent approximately 30% of the overall population. Assuming that 30% of the participants in the overall population are at increased risk of severe RSV disease (~870 participants), the observation of 0 events in participants at increased risk of severe RSV disease would be associated with 95% confidence that the true rate is less than 0.4%.

Table 7 shows the probabilities of observing at least one AE in one of the arms at given true AE rates in the Safety Subset (overall population and participants at increased risk of severe RSV disease).

Table 7: Probability of Observing at Least One Adverse Event or Serious Adverse Event at a Given True Adverse Event Rate in the Safety Subset

True Adverse Event Rate	Probability of Observing at Least One Adverse Event in N Participants			
	Overall N=350	Overall N=2,900	Increased Risk N=175	Increased Risk N=870 ^a
0.1%	30%	95%	16%	58%
0.5%	83%	100%	58%	99%
1%	97%	100%	83%	100%
2.5%	>99.9%	100%	99%	100%

^a Approximate number

11.2.4. Revaccination Subcohorts

Immunogenicity

Immunogenicity will also be assessed in participants of the Revaccination Subcohorts, which consist of ~120 participants (Revaccination Subcohorts A and C) or ~135 participants (Revaccination Subcohort B) who received active study vaccine on Day 1 and ~120 participants (Revaccination Subcohorts A and C) or ~135 participants (Revaccination Subcohort B) who received placebo on Day 1 for a total of ~750 participants. All participants in the Revaccination Subcohorts will receive a second vaccination with active study vaccine: on Day 365 (Month 12) (Revaccination Subcohort A), on Day 730 (Month 24) (Revaccination Subcohort B), or on Day 1,095 (Month 36) (Revaccination Subcohort C).

The geometric mean of the titer ratios (GMRs) between Day 15 post first vaccination and Day 15 post second vaccination within a group, as well as the ratio of Day 15 post second vaccination between the 2 groups (active study vaccine versus placebo on Day 1), for the different assays will be calculated.

Table 8 shows the actual distance from the mean to the limits of 95% CI around the ratio between Day 15 post first vaccination and Day 15 post second vaccination within a group for the different assays. The calculations consider an exclusion rate of ~10% from the sample size of revaccinated

participants (~108 participants per group for Revaccination Subcohorts A and C, and ~120 participants per group for Revaccination Subcohort B).

Table 8: Distance From the Mean to the Limits of 95% CI Around the Ratio Between Day 15 Post First Vaccination and Day 15 Post Second Vaccination Within a Group for Pre-F ELISA, VNA A2, and ELISpot

Revaccination Subcohort	Assay	N (per group)	Distance ^a from Mean to Limits 95%CI	95% CI if Observed Ratio is 1
A and C	Pre-F ELISA (SD=1.3)	120	0.248	(0.84;1.19)
	VNA A2 (SD=1.5)	120	0.286	(0.82;1.22)
	ELISpot (SD=1.2)*	50	0.341	(0.79; 1.27)
B	Pre-F ELISA (SD=1.3)	135	0.235	(0.85; 1.18)
	VNA A2 (SD=1.5)	135	0.271	(0.83; 1.21)
	ELISpot (SD=1.2)	135	0.217	(0.86;1.16)

CI = confidence interval, ELISA = enzyme-linked immunosorbent assay, ELISpot = enzyme-linked immunospot (assay), SD = standard deviation, VNA = virus neutralization assay

^a Calculated on the log₂-scale assuming a correlation of 0.5 between the 2 timepoints.

*: No PBMC samples are taken for Revaccination Subcohort A.

Table 9 shows the actual distance from the mean to the limits of 95% CI around the Day 15 post second vaccination ratio between the 2 groups, for the different assays. The calculations consider an exclusion rate of 10% from the sample size of revaccinated participants (~108 participants per group for Revaccination Subcohorts A and C, and ~120 participants per group for Revaccination Subcohort B).

Table 9: Distance From the Mean to the Limits of 95% CI Around the Ratio on Day 15 Post Second Vaccination Between the 2 Groups for Pre-F ELISA, VNA A2, and ELISpot

Revaccination Subcohort	Assay	N (per group)	Distance ^a from Mean to Limits 95% CI	95% CI if Observed Ratio is 1
A and C	Pre-F ELISA (SD=1.3)	120	0.349	(0.79;1.27)
	VNA (SD=1.5)	120	0.402	(0.76;1.32)
	ELISpot (SD=1.2)*	50	0.476	(0.72; 1.39)
B	Pre-F ELISA (SD=1.3)	135	0.331	(0.79;1.26)
	VNA A2 (SD=1.5)	135	0.381	(0.77; 1.30)
	ELISpot (SD=1.2)	135	0.305	(0.81; 1.24)

CI = confidence interval, ELISA = enzyme-linked immunosorbent assay, ELISpot = enzyme-linked immunospot (assay), SD = standard deviation, VNA = virus neutralization assay

^a Calculated on the log₂-scale.

*: No PBMC samples are taken for Revaccination Subcohort A.

Safety

With ~240 active study vaccine participants in Revaccination Subcohorts A and C, and ~270 active study vaccine participants in Revaccination Subcohort B, the observation of 0 events in the database would be associated with 95% confidence that the true rate is <1.5%.

Table 10 shows the probabilities of observing at least 1 AE in one of the arms at given true AE rates in the Revaccination Subcohorts.

Table 10: Probability of Observing at Least 1 Adverse Event or Serious Adverse Event at a Given True Adverse Event Rate in the Revaccination Subcohorts

True Adverse Event Rate	Revaccination Subcohorts A and C		Revaccination Subcohort B	
	Overall	Per Group	Overall	Per Group
	N=240 ^a	N=120 ^a	N=270 ^a	N=135 ^a
0.1%	21%	11%	24%	13%
0.5%	70%	45%	74%	49%
1%	91%	70%	93%	74%
2.5%	>99.9%	95%	100%	97%

^a Approximate number

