eDiary training and distribution ⁱ	● ^o						
Thermometer training and distribution	●						
Ruler training and distribution	●						
Verification of selected eligibility criteria	❶ ^q						
Contraindications to vaccination	❶						
Vaccination	●						
30 minute post vaccination observation ^s	●						
Solicited AE recording ^t	●	●					
Unsolicited AE recording ^u	Continuous						
SAEs ^v	Continuous until the end of the first RSV season (or 6 months after vaccination, whichever comes later), and from revaccination on Day 730 until 6 months after revaccination^{dd}						
AESIs ^v	Continuous from revaccination on Day 730 until 6 months after revaccination^{dd}						
AEs and special reporting situations related to study procedures and non investigational (concomitant) Janssen products	Continuous until the end of the participant's study participation						
AEs leading to discontinuation (from study)	Continuous until the end of the participant's study participation						
Concomitant medications ^{w,x}	Continuous until the end of the participant's study participation^z						
eDiary review of solicited AEs by study staff		●					
Humoral immunity sample, mL	❶ 20	20	20	20	20	20	20
Cellular immunity sample, mL (at certified sites)	❶ 40		40	40	40	40	40
Paxgene sample, mL	❶ 2.5	2.5					
Blood Draw Volumes							
Approx. daily blood draw, mL	62.5	22.5	60	60	60	60	60
Approx. cumulative blood draw, mL	107.5	130	190	250	310	370	430

❶ pre-dose; ❷ any seasonal influenza vaccination must occur at least 14 days before or at least 14 days after any study vaccination; SARS-CoV-2 vaccination must occur as follows: Live-attenuated SARS-CoV-2 vaccine: at least 28 days before or at least 28 days after study vaccination; Non-live SARS-CoV-2 vaccine: at least 14 days before or at least 14 days after study vaccination; Viral-vectored SARS-CoV-2 vaccine: at least 28 days before or at least 28 days after study vaccination

The  symbol may refer to a telephone call or a telemedicine interview/contact.

Footnotes:

- a. The visit day is relative to the actual day of vaccination in the first RSV season. The timing of the visit day is determined by the visit window relative to the last vaccination.
- b. Signing the ICF should be done before any study-related activity on Day 1 and resigned on Day 365 and no later than at the end of the second RSV season.

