Under Amendment 8 (dated 16 February 2023), Revaccination Subcohort D (ie, participants who would have received a revaccination with the Ad26.RSV.preF/RSV preF protein mixture at 4 years after the first vaccination) will be removed as additional data with a Month 48 revaccination timepoint are not expected to provide novel insights on the kinetics of the immune response after revaccination with the Ad26.RSV.preF/RSV preF protein mixture.

A graphical display of all Revaccination Subcohorts is presented in [Figure 5](#) for Group 1 (active study vaccine on Day 1) and in [Figure 6](#) for Group 2 (placebo on Day 1).

Note: Participants can be enrolled in both the Safety and the Immuno Subset. Participants in Revaccination Subcohorts A and B cannot have participated in the Safety or the Immuno Subset.

Study duration will be approximately 2.6 years for participants in the first cohort. Study duration in the Revaccination Subcohorts will be 2 years for participants in Revaccination Subcohort 1A, 3 years for participants in Revaccination Subcohorts 2A and 1B, and 4 years for participants in Revaccination Subcohorts 2B and C.

If the study does not progress to a second RSV season, the study duration will be approximately 0.6 years. If the study does not progress to a third RSV season, the study duration will be approximately 1.6 years.

The study will continue with Revaccination Subcohort C depending on the 28-day post second vaccination analysis results from Revaccination Subcohort B.

Study duration will be approximately 0.6 years for the potential 2,000 extra participants in the second cohort.

The end of the study is defined as the last participant's last visit.

Table 2: Study Design: VAC18193RSV2001

Cohort/Group/ Subcohort	Day 1 Vaccination	Day 365 (Month 12) Revaccination	Month 24 Revaccination	Month 36 Revaccination
		(Amendment 4)		(Amendment 5)
Cohort 1^{a,b} N=5,800				
Group 1 N=2,900	Active vaccine mixture Safety Subset^c (N 350) Immuno Subset^c (N 100)			
Revaccination Subcohort 1A^c (N=120)	Active vaccine mixture	Active vaccine mixture		
Revaccination Subcohort 1B^c (N=135)	Active vaccine mixture		Active vaccine mixture	
Revaccination Subcohort 1C^{c,d} (N=120)	Active vaccine mixture			Active vaccine mixture
Group 2 N=2,900	Placebo Safety Subset^c (N 350) Immuno Subset^c (N 100)			
Revaccination Subcohort 2A^c (N=120)	Placebo	Active vaccine mixture	Ad26.RSV.preF alone (N=40)	
			RSV preF protein alone (N=40)	

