9.2.2. Immunogenicity Evaluations

Venous blood samples of approximately 15 mL and 40 mL will be collected for the determination of humoral and cellular immune responses, respectively. Timings of blood draws are specified in the Schedule of Activities. Sample collection and processing will be performed according to current versions of approved standard operating procedures.

Immunogenicity assessments may include, but are not limited to, the humoral and cellular immunogenicity assays (as available and applicable) summarized in [Table 4](#) and [Table 5](#) below.

Humoral immune responses will be assessed in participants experiencing an ARI episode, participants in the Immuno Subset (ie, 200 randomized participants, 100 per group), and participants in the Revaccination Subcohorts (ie, approximately 240 participants, 120 per group [Revaccination Subcohorts A and C]; or approximately 270 participants, 135 per group [Revaccination Subcohort B]).

Cellular immune responses will be assessed in the Immuno Subset and in all participants (at certified sites) in Revaccination Subcohort 2A after the third vaccination and in Revaccination Subcohort B after the second and third vaccination. Cellular immune responses will be assessed in a subset of approximately 100 participants (approximately 50 per group) in Revaccination Subcohort C.

Table 4: Summary of Immunogenicity Assays (Humoral)

Assay	Purpose
Secondary endpoints	
RSV neutralization A	Analysis of neutralizing antibodies to an A strain
F protein antibodies (ELISA; pre-F and/or post-F)	Analysis of antibodies binding to RSV F protein in pre-fusion and/or post-fusion form
Exploratory endpoints	
RSV strain cross-neutralization	Analysis of cross-neutralizing antibodies to B and/or a different A strain(s)
F protein antibody specificity characterization	Pre- and post-F specificity by binding or functional assays such as ELISA, and/or competition ELISA. Adsorption of serum with pre-F and post-F protein before any antibody assay, epitope mapping, functional VNAs
G protein antibodies (ELISA)	Analysis of antibodies binding to RSV G protein
Adenovirus neutralization assay	Analysis of neutralizing antibodies to adenovirus
Functional and molecular antibody characterization	Analysis of antibody characteristics including, but not limited to, ADCC, ADCP, avidity, other respiratory viral neutralizing or binding assays, Ig isotype, functional VNAs to other respiratory viruses, and antibody assessments for antibody repertoire

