11.9.2. Revaccination Subcohorts

No formal hypothesis on immunogenicity will be tested for Revaccination Subcohorts. Descriptive statistics (geometric mean and 95% CI for ELISA and RSV neutralization assay, median and quartiles for IFN- γ ELISpot) will be calculated for continuous immunologic parameters at all time points. Geometric mean fold rises from baseline and corresponding 95% CIs might additionally be calculated. Geometric mean ratios and corresponding 95% CIs between Day 15 post first vaccination and Day 15 post second vaccination within the group receiving active study vaccine

on Day 1 and the day of the second vaccination depending on the Revaccination Subcohort will be calculated for the different assays.

In addition, the GMT ratios with corresponding 95% CIs of Day 15 post second vaccination for the group receiving active study vaccine twice versus the group receiving placebo first and active study vaccine 1, 2, or 3 years later will also be calculated for the different assays. Therefore, an analysis of variance (ANOVA) model will be fitted with the respective titers as dependent variable and group as independent variable. The estimate and CIs obtained as such will be back transformed (by exponentiation) to a GMT ratio and the corresponding CI. As a sensitivity analysis, different variances between the groups will be allowed, therefore the CIs will be calculated via Welsh's ANOVA.

For Revaccination Subcohorts 2A and 2B that get a third vaccination with Ad26.RSV.preF/RSV preF protein mixture or with the individual vaccine components, no formal hypothesis is tested; descriptive statistics over time after the third vaccination will be calculated.

Graphical representations of immunologic parameters will be made as applicable.

The impact of baseline factors on the humoral responses will be explored graphically or via descriptive statistics.

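### Table 8 gives a precision for the ELISpot ratio of Day 15 after the second to Day 15 after the first vaccination that Subcohort 1B cannot supply and that Subcohort 1C supplies only under an unstated overlap with the Immuno Subset

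*Protocol*

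**What the plan says.** Protocol Section 11.2.4 introduces Table 8 as the distance from the mean to the 95% CI limits "around the ratio between Day 15 post first vaccination and Day 15 post second vaccination within a group for the different assays". The table lists pre-F ELISA, VNA A2 and ELISpot. Its ELISpot rows are:

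- Subcohort B: N=135 per group, 0.217, CI 0.86 to 1.16 around an observed ratio of 1.
- Subcohorts A and C: N=50, 0.341, CI 0.79 to 1.27. A footnote says that no PBMC are taken in A, so the row concerns C.

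The half-widths are calculated "assuming a correlation of 0.5 between the 2 timepoints". The synopsis carries the same table.

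Section 11.9.2 turns this into an analysis: "Geometric mean ratios and corresponding 95% CIs between Day 15 post first vaccination and Day 15 post second vaccination within the group" given active vaccine on Day 1, for the different assays. ELISpot is among the assays named in that paragraph.

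On sampling, Section 9.2.2 says that cellular responses in the Revaccination Subcohorts are assessed "in Revaccination Subcohort 2A after the third vaccination and in Revaccination Subcohort B after the second and third vaccination", and in about 50 participants per group in C. Section 3.1 adds: "Participants in Revaccination Subcohorts A and B cannot have participated in the Safety or the Immuno Subset".

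**The concern.** A paired ratio needs an ELISpot value at both time points in the same participant. Table 8 relies on this through its within-person correlation. If the first value was never collected, neither the ratio nor its stated precision exists.

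The stake is the cellular part of the exploratory objective on immunogenicity after revaccination at 2 or 3 years. A reader of Table 8 would expect a cellular booster comparison in B with a CI of about ±15% around the ratio, and the study cannot deliver it. The only PBMC caveat in the table concerns Subcohort A, so the gap in B is not disclosed.

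**Working it through.** **1. Reproducing the stated figures.** Inputs are from Section 11.2.4: ELISpot SD 1.2 on the log2 scale, correlation ρ = 0.5, two-sided 95% CI, and about 120 evaluable per group in B after roughly 10% exclusions.

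Half-width d = t(0.975, n−1) × SD × √(2(1−ρ)) / √n. With ρ = 0.5 the factor √(2(1−ρ)) equals 1.

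- B, n=120: d = 0.2169 (stated 0.217); 2^±d gives 0.86 to 1.16.
- C, n=50: d = 0.3410 (stated 0.341); 2^±d gives 0.79 to 1.27.

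The humoral rows reproduce too: 0.248 and 0.286 at n=108, and 0.235 and 0.271 at n=120. The arithmetic is right, so the question is whether the pairs exist.

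**2. Pairs in Subcohort 1B.**

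- Schedule of Activities, Cohort 1: cellular blood after the Day 1 vaccination, including Day 15, comes only from Immuno Subset participants.
- Section 3.1 and the 1B and 2B schedules: B participants cannot have been in that subset.
- 1B schedule: Days 1 and 15 carry a 15 mL humoral sample only. The cellular row first has an entry pre-dose on Day 730.
- Blood volume: 15 + 15 + 15 = 45 mL up to Day 365, then 62.5 + 22.5 + 5 × 60 = 385 mL from Day 730. The sum is 430 mL, the total stated for 1B. A 40 mL cellular draw on Day 15 is not in it.

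The number of pairs is 0.

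**3. Pairs in Subcohort 1C.** The C schedule starts its own cellular sampling at Day 1,095. C participants may, however, have been in the Immuno Subset: the schedule lists Visits 2b, 2c, 5 and 8 for such members and refers to the Cohort 1 schedule for details. Those members gave cellular blood on Day 15. The protocol states neither how many entered C nor how the roughly 50 per group for cellular sampling are chosen. The stated 0.341 needs all 50 to have been Immuno Subset members, which is half of the approximately 100 active participants in that subset.

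The same formula at smaller numbers of pairs gives:

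| Pairs in 1C | Half-width (log2) | 95% CI if ratio is 1 |
|---|---|---|
| 50 | 0.341 | 0.79 to 1.27 |
| 25 | 0.50 | 0.71 to 1.41 |
| 10 | 0.86 | 0.55 to 1.81 |
| 4 | 1.91 | 0.27 to 3.76 |

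The C row also uses n=50 without the roughly 10% exclusion that the text says was applied; n=45 would give 0.361.

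**The case against.** **The ratio may be meant for humoral assays only, or left to the SAP.** Section 11.2.4 speaks of titer ratios, and detail can follow in the SAP. But Table 8 has ELISpot rows for exactly this ratio, and no SAP can supply a sample that was never drawn.

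**Subcohort C.** A reader might infer that most of C has no Day 15 cellular value and that the ratio fails there as well. The documents do not support this. The bar on Immuno Subset members covers only A and B, and 50 pairs is numerically possible. The 360 mL total for C's cellular participants (4 × 15 + 5 × 60) contains no Day 15 cellular draw, but the C schedule omits Immuno Subset draws throughout, so the total settles nothing. Overlap in proportion to group size would give about 4 of 120 (120 × 100/2,900 = 4.1). That is only an assumption, because the Immuno Subset came from selected sites. What stands is that the overlap is unstated.

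**Subcohort 2B.** Table 8 is per group, so a reader might count 2B as a second lost group. Section 11.9.2 limits this ratio to participants given active vaccine on Day 1, so only 1B is affected.

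**Certified sites.** Cellular samples in B are taken at certified sites, which makes 135 an upper bound for any ELISpot analysis. Nothing says that any B participant is at an uncertified site, so a shortfall is not shown.

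**Other contrasts remain.** This stands. Section 11.9.2 keeps descriptive ELISpot summaries at all time points, optional fold rises from baseline, and the between-group ratio at Day 15 after the second vaccination, with precision in Table 9.

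**Conclusion.** The point holds for Subcohort 1B without any assumption: the planned ELISpot ratio has 0 pairs, and the half-width of 0.217 describes an analysis that cannot be done. For Subcohort 1C the point is narrower. The stated 0.341 is conditional on an overlap of 50 with the Immuno Subset that the protocol permits but does not give; the half-width would be 0.50 at 25 pairs and 0.86 at 10, on the protocol's own SD and correlation.

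The humoral rows of Table 8 and the between-group ELISpot comparison of Table 9 are not affected by the missing first-vaccination sample. Immunogenicity in the Revaccination Subcohorts is exploratory and descriptive, no hypothesis is tested on it, and the efficacy and safety conclusions do not depend on it. It should be fixed, but a reader should not infer that it threatens the trial's main conclusions.

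**What to change.** - **Subcohort B:** delete the ELISpot row from Table 8 and the synopsis copy. In Sections 11.2.4 and 11.9.2 and the synopsis, limit the Day 15-to-Day 15 ratio in B to the humoral assays.
- **Subcohort C:** restrict the ELISpot ratio to participants with an Immuno Subset Day 15 sample, and restate N and the half-width for the expected overlap. If no overlap is planned, delete the row.
- **ELISpot in B and C:** make firm the fold change from the pre-revaccination sample (Day 730 or Day 1,095) to Day 15 after revaccination, which Section 11.9.2 now leaves optional. Report it alongside the Table 9 between-group ratio.

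The cost is wording in Sections 11.2.4 and 11.9.2 and the synopsis. Every sample needed is already scheduled.
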